9.2.3. Birth outcomes (major congenital malformations and small size for gestational age)

Separate cohorts of pregnant women exposed to Pfizer-BioNTech bivalent COVID-19 Vaccine (exposed cohort) and pregnant women not exposed to any COVID-19 vaccine (unexposed cohort) will be formed for the analysis of birth outcomes (Table 2). To be eligible for either cohort, women must have had a singleton pregnancy ending in a livebirth and must have had continuous enrollment from 12 months before the index date until birth. The index date in both exposed and unexposed women will be the LMP date. Analyses will be limited to pregnant women whose singleton pregnancies have ended in a livebirth and who have been successfully linked to an infant.

Table 2. Cohort definitions for analysis of birth outcomes

Cohort	Eligibility criteria
Exposed cohort	
 Pregnancy ending in a livebirth, with continuous enrollment in the 12 months before the index date (LMP) until birth Pregnancy linked to at least 1 infant Receipt of Pfizer-BioNTech bivalent COVID-19 Vaccine during the outcome-specific exposure window (as defined in Table 3)
Unexposed cohort	
 Pregnancy ending in a livebirth, with continuous enrollment in the 12 months before the index date (LMP) until birth Pregnancy linked to at least 1 infant

PFIZER CONFIDENTIAL

Table 2. Cohort definitions for analysis of birth outcomes

Cohort	Eligibility criteria
	
 No receipt of any COVID-19 vaccine during the outcome-specific exposure window (as defined in Table 3) Matched individually (in a ratio of at least 1:1) to exposed women on LMP, maternal age, and US state (if feasible, or broader geographic region if not feasible)

COVID-19 = coronavirus disease 2019; LMP = date of last menstrual period. US = United States

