9.2.4.2. Pregnancy and birth outcomes

For analysis of pregnancy outcomes, pregnant women will be followed from the index date until the earliest of the following: end of pregnancy, latest gestational age at which an outcome can occur (applies only to stillbirth and preterm birth), or receipt of another dose of any COVID-19 vaccine other than Pfizer-BioNTech bivalent COVID-19 Vaccine ([Table 4](#)).

PFIZER CONFIDENTIAL

CT24-WI-GL02-RF02 4.0 Non-Interventional Study Protocol Template For Secondary Data Collection Study
 01-Jun-2022

For analysis of birth outcomes, infants will be followed for events from birth until 12 months after birth (for major congenital malformations) or until 1 month after birth (for small size for gestational age) (Table 4).

Table 4. Follow-up for pregnancy outcomes and birth outcomes

Safety event	Start of follow-up	End of follow-up
Pregnancy outcomes		
Spontaneous abortion	Index date (as defined in Table 1)	Earliest of the following: 
 • Occurrence of spontaneous abortion • 20 weeks of gestation (latest gestational age at which a spontaneous abortion can occur) • Other event marking the end of pregnancy (ectopic pregnancy or pregnancy termination); to be treated as competing events • Receipt of another dose of COVID-19 vaccine other than Pfizer-BioNTech bivalent COVID-19 Vaccine
Stillbirth	Index date (as defined in Table 1)	Earliest of the following: 
 • Occurrence of stillbirth • Other event marking the end of pregnancy (ectopic pregnancy, spontaneous abortion, pregnancy termination, or livebirth); to be treated as competing events • Receipt of another dose of COVID-19 vaccine other than Pfizer-BioNTech bivalent COVID-19 Vaccine
Preterm birth	Index date (as defined in Table 1)	Earliest of the following: 
 • Occurrence of preterm birth (ie, livebirth before 37 completed weeks of gestation) • 37 weeks of gestation (latest gestational age at which a preterm birth can occur) • Other event marking the end of pregnancy (ectopic pregnancy, spontaneous abortion, pregnancy termination, stillbirth); to be treated as competing events • Receipt of another dose of COVID-19 vaccine other than Pfizer-BioNTech bivalent COVID-19 Vaccine
Birth outcomes		

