Major congenital malformations	Birth	Earliest of the following (in the infant): 
 • Diagnosis of major congenital malformation • End of the study period • End of data availability • Death • 12 months after birth
Small size for gestational age	Birth	Earliest of the following (in the infant): 
 • Diagnosis of small size for gestational age • End of the study period • End of data availability • Death • 1 month after birth

COVID-19 = coronavirus disease 2019.

090177e19f732934\Approved\Approved On: 14-Dec-2023 13:35 (GMT)

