9.7.2. Analysis of pregnancy and birth outcomes

Among pregnant women, the distribution of demographics, comorbidities, and other potential confounders will be reported and compared between the matched exposed and unexposed cohorts. Covariate balance in the matched and weighted cohorts will be assessed using standardized differences or other suitable methods.

Vaccinated pregnant women will be matched to pregnant unexposed comparators in a ratio of exposed:unexposed of at least 1:1 on maternal age, US state (if feasible, or broader geographic region if not feasible), and pregnancy start (to address confounding by calendar time). Confounding by other variables will be addressed using inverse probability of treatment weighting, based on propensity scores estimated in the matched population.

In each data RP, measures of incidence or prevalence of pregnancy and birth outcomes and associated 95% CIs will be estimated within the matched exposed and unexposed cohorts.

Cox models or Poisson regression will be used to calculate adjusted HRs or incidence rate ratios and 95% CIs for spontaneous abortion, stillbirth, and preterm birth. For major congenital malformations and small size for gestational age, logistic regression will be used to estimate PORs and 95% CIs.

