Similar to other claims and electronic health records databases in the US, an additional limitation of the data sources proposed for this study is that a substantial proportion of individuals may lack enrollment from the initial authorization of COVID-19 vaccines (on 10 December 2020) until the index date; long-term enrollment would be necessary to definitively assess prior completion of a primary vaccine series based on a patient's recorded history of COVID-19 vaccines in claims/administrative data. Within the Sentinel Distributed Database, only 47% of individuals have ≥ 2 years continuous database enrollment, with 36% of individuals enrolled for at least 2.5 years (Sentinel, 2023b). This may severely limit the ability to identify receipt of the bivalent vaccine as a primary series versus booster dose.

Another data source–related limitation is that the identification of outcomes and covariates in claims data and electronic health records data is based on algorithms and is subject to misclassification (eg, false positives, false negatives). There have been limited validation studies of *International Classification of Diseases, 10th Revision, Clinical Modification* (ICD-10-CM)-based algorithms for safety events of interest, and the accuracy of algorithms for many safety events of interest is unknown. When possible, validated algorithms will be used. However, some events, such as spontaneous abortion, are particularly at risk of misclassification, because early pregnancy losses may not be recognized in claims or even by the individual. If prior studies have not demonstrated adequate performance of the algorithm for myocarditis/pericarditis, a quantitative bias analysis will be performed to assess the potential impact of outcome misclassification on comparative risk estimates for myocarditis/pericarditis based on ongoing validation studies. Capture of non-severe and asymptomatic COVID-19 is anticipated to be substantially incomplete due to the high prevalence of at-home testing, non-medically attended COVID-19, and incomplete capture of laboratory results in the Sentinel Distributed Database. History of COVID-19 (which is a covariate and subgroup of interest for the study) will therefore be limited to severe COVID-19, defined using inpatient diagnoses of COVID-19.

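### The malformation analysis seeks cases for 12 months but requires enrolment only to birth and ignores observed time, so infants who leave the plan early with nothing coded count as non-cases

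*Protocol*

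**What the plan says.** - **Eligibility (Section 9.2.3, Table 2).** Both birth-outcome cohorts need "Pregnancy ending in a livebirth, with continuous enrollment in the 12 months before the index date (LMP) until birth". The only infant-side criterion is "Pregnancy linked to at least 1 infant", and the analysis set is singleton livebirths in women "who have been successfully linked to an infant". No enrolment of the infant after birth is required.
- **Ascertainment (Section 9.2.4.2).** The text states that "infants will be followed for events from birth until 12 months after birth (for major congenital malformations". For small size for gestational age the window is only 1 month, so this point concerns malformations.
- **End of infant follow-up (Table 4).** Besides diagnosis, death, study end and 12 months, follow-up can stop at "End of data availability".
- **Analysis (Section 9.7.2).** Measures of prevalence "will be estimated within the matched exposed and unexposed cohorts", and "logistic regression will be used to estimate PORs and 95% CIs". No person-time, censoring or weighting for incomplete infant follow-up is stated.
- **Turnover (Section 9.9).** In the Sentinel database "only 47% of individuals have ≥ 2 years continuous database enrollment", and 36% have at least 2.5 years. The protocol raises this only as a limit on telling primary-series from booster doses. Infants leaving the plan are not discussed.

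**The concern.** A malformation first coded at month 6 can be found only if the infant is still in the plan at month 6. The cohort is closed at birth, the search runs to 12 months, and the model treats the result as a yes/no outcome for every linked infant. The Table 4 end dates therefore shorten the search for an infant who leaves but do not affect how that infant enters the denominator. Someone lost at month 2 with no code looks the same as someone observed for a full year without a malformation.

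Two results are exposed. Research question 3 asks for the prevalence in each cohort, which would be too low for a 12-month definition. Primary objective 3 asks for the POR, which would pick up any difference in plan retention between exposed and unexposed families. Section 9.7.3.3 itself expects unvaccinated women to differ in health-seeking behaviour, so equal retention is something to check rather than assume.

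Other parts of the protocol do tie enrolment to the outcome window. Section 9.2.1.1 requires it to the end of the control interval or death, and Section 9.2.2 to the end of pregnancy.

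**Working it through.** **1. The plan's own figure.** Section 9.5.2 gives 90% power for OR 1.2, 3% in the unexposed, 20,000 per group, two-sided 0.05.
- Exposed rate: odds = 1.2 × 0.03/0.97, so p1 = 0.0358.
- Two-proportion normal approximation: power = 0.900. The figure reproduces.

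**2. Share of cases missed.** The documents give neither infant retention nor the timing of first codes, so both are assumed. Let leaving be exponential at rate h per year, and let a share f of malformations be first coded evenly over months 1-12.
- Mean coverage over months 1-12: c = [exp(-h/12) - exp(-h)] / (h × 11/12)
- Missed share = f × (1 - c)

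The protocol's figures describe members in general. Three ways of borrowing them give a range for h:

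| Borrowed figure | h | 12-month retention exp(-h) | c | Missed, f = 20% / 40% / 60% |
|---|---|---|---|---|
| Slope from 47% to 36% (9.9): ln(0.47/0.36)/0.5 | 0.53 | 59% | 0.757 | 5% / 10% / 15% |
| From time zero (9.9): -ln(0.47)/2, or -ln(0.36)/2.5 | 0.38-0.41 | 69-66% | 0.819-0.806 | 4% / 7-8% / 11-12% |
| Mean enrolment 55.3 months in one partner (9.4.4): 12/55.3 | 0.22 | 80% | 0.891 | 2% / 4% / 7% |

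Over these assumptions, roughly 2-15% of cases are missed.

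**3. Equal leaving in both cohorts.** Multiply both true rates by the same recorded share s, starting from 3.00% and OR 1.2.
- s = 0.95: unexposed 2.85%, POR 1.1996, power 0.885
- s = 0.90: unexposed 2.70%, POR 1.1993, power 0.867
- s = 0.85: unexposed 2.55%, POR 1.1989, power 0.847

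Prevalence falls and power drops slightly. The POR hardly moves.

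**4. Unequal leaving, true POR 1.0, 20-point gap (assumed).**
- *Retention 75% exposed, 55% unexposed, model of step 2.* c = 0.858 and 0.733. Recorded shares (1 - f + f × c) are 0.957 and 0.920 at f = 30%, ratio 1.04; and 0.929 and 0.866 at f = 50%, ratio 1.07. At 3% prevalence the POR is almost the same as this ratio.
- *10% leaving in the exposed, 30% in the unexposed, with a share m of leavers' malformations first coded after they left.* m = 25%: 0.975/0.925, POR 1.06. m = 50%: 0.95/0.85, POR 1.12.
- *The same with 30% and 10% reversed.* POR 0.95 and 0.89.

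So a 20-point gap moves a null POR by roughly 4-12%, and the sign follows the direction of the gap.

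**The case against.** The strongest reply is that no sentence says an infant lost at month 2 is counted as malformation-free. Table 4 has the form of a censoring scheme, and Section 9.7 leaves detailed methodology to the SAP, which is not at hand and could add a rule. It stands that the SAP can repair this. But the protocol itself fixes the cohort, the window and the model. It expressly defers items such as control intervals, washout periods and the pregnancy algorithm, but not this one. Followed as written, it gives the result described. The year of infant follow-up anticipated in Section 6 is calendar time and does not keep an infant in the plan.

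Three stronger readings are tempting, and the documents do not support them:
- **That the protocol implies a loss of 0.53 per year.** The enrolment shares in Section 9.9 cover all Sentinel members, not infants, and 0.53 is the steepest reading of them. From time zero they give 0.38-0.41, and the 55.3-month mean gives 0.22. That mean comes from a partner with a median age of 67, so it does not transfer directly either.
- **That the POR is biased.** With equal leaving it is essentially unchanged. No retention gap is documented, and its direction is unknown. Both cohorts need about 21 months of maternal enrolment by birth, are matched on LMP, maternal age and region, and are weighted on comorbidity and healthcare use. All of this should narrow a gap.
- **That observed cases must fall below the 3% used for power.** That rate is applied jointly to both birth outcomes and is not stated to be the true 12-month malformation prevalence. It may already be an as-recorded rate.

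**Conclusion.** The point holds on the text. Eligibility ends at birth, ascertainment runs to 12 months, and the stated analyses do not use observed time. The sure consequence, whenever a leaver's malformation would have been coded after leaving, is that 12-month prevalence is understated in both cohorts, with a small loss of power: from 90% to about 87% if 10% of cases go unrecorded and 3% is taken as the true rate.

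Material bias in the POR is conditional on infant retention differing by exposure. It could go either way, and no planned output would reveal it.

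The magnitudes rest on assumptions the documents cannot confirm. These are 12-month retention of 59-80%, 20-60% of malformations first coded after the first month, and, for the POR, a 20-point retention gap. Under them, 2-15% of cases are missed and a null POR shifts by roughly 4-12%. The analysis should be amended because the outcome belongs to a primary objective and the remedy is cheap, not because a large bias has been shown.

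**What to change.** In Section 9.7.2, for major congenital malformations:

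1. Account for infant disenrolment before 12 months. Either add inverse-probability-of-censoring weights to the weighted logistic model, or estimate 12-month cumulative prevalence in each weighted cohort with censoring at the end of the infant's enrolment and derive the POR from it.
2. Report the duration of infant enrolment by cohort, so that a retention gap is visible.
3. Add a sensitivity analysis restricted to infants enrolled for 12 months or until death, with the same rule for infants with and without a malformation.

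The cost is protocol and SAP wording, modest programming on enrolment data the partners already capture (Section 9.4), slightly wider intervals, and a smaller sample in the sensitivity analysis. The restriction should stay a sensitivity analysis. As the primary rule it would drop every leaver, and at OR 1.2 and 3% it would take power from 90% to 83% with 20% leaving or 71% with 40% leaving (assumed shares; 16,000 or 12,000 infants per group). The change should be settled before the final-analysis queries go out, which Section 6 anticipates in the second quarter of 2026.

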9.2.3.1. Exposure windows for analyses in pregnant women

Outcome-specific exposure windows are provided in Table 3. For pregnancy and birth outcomes, only women who were exposed to Pfizer-BioNTech bivalent COVID-19 Vaccine during outcome-specific exposure windows will be eligible for the exposed cohorts. For each pregnancy and birth outcome, the exposure window will be from 28 days before pregnancy start until the end of the outcome-specific risk period (as defined in [Section 9.3.2.2](#)).

Table 3. Exposure windows for analysis of pregnancy outcomes and birth outcomes

Type of safety event	Safety event of interest	Exposure window
Pregnancy outcomes	Spontaneous abortion	From 28 days before LMP until 19 weeks and 6 days of gestation
	Stillbirth	From 28 days before LMP until pregnancy end
	Preterm birth	From 28 days before LMP until 36 weeks and 6 days of gestation
Birth outcomes	Major congenital malformations	From 28 days before LMP until the last day of the first trimester
	Small size for gestational age	From 28 days before LMP until pregnancy end

LMP = date of last menstrual period.

9.2.4. Follow-up

9.2.4.1. General safety outcomes

Individuals will be followed from the start of the risk interval (the index date or day after the index date, depending on the outcome) until the end of the control interval (to be defined in the SAP).

9.2.4.2. Pregnancy and birth outcomes

For analysis of pregnancy outcomes, pregnant women will be followed from the index date until the earliest of the following: end of pregnancy, latest gestational age at which an outcome can occur (applies only to stillbirth and preterm birth), or receipt of another dose of any COVID-19 vaccine other than Pfizer-BioNTech bivalent COVID-19 Vaccine ([Table 4](#)).

PFIZER CONFIDENTIAL

CT24-WI-GL02-RF02 4.0 Non-Interventional Study Protocol Template For Secondary Data Collection Study
 01-Jun-2022

For analysis of birth outcomes, infants will be followed for events from birth until 12 months after birth (for major congenital malformations) or until 1 month after birth (for small size for gestational age) (Table 4).

Table 4. Follow-up for pregnancy outcomes and birth outcomes

Safety event	Start of follow-up	End of follow-up
Pregnancy outcomes		
Spontaneous abortion	Index date (as defined in Table 1)	Earliest of the following: 
 • Occurrence of spontaneous abortion • 20 weeks of gestation (latest gestational age at which a spontaneous abortion can occur) • Other event marking the end of pregnancy (ectopic pregnancy or pregnancy termination); to be treated as competing events • Receipt of another dose of COVID-19 vaccine other than Pfizer-BioNTech bivalent COVID-19 Vaccine
Stillbirth	Index date (as defined in Table 1)	Earliest of the following: 
 • Occurrence of stillbirth • Other event marking the end of pregnancy (ectopic pregnancy, spontaneous abortion, pregnancy termination, or livebirth); to be treated as competing events • Receipt of another dose of COVID-19 vaccine other than Pfizer-BioNTech bivalent COVID-19 Vaccine
Preterm birth	Index date (as defined in Table 1)	Earliest of the following: 
 • Occurrence of preterm birth (ie, livebirth before 37 completed weeks of gestation) • 37 weeks of gestation (latest gestational age at which a preterm birth can occur) • Other event marking the end of pregnancy (ectopic pregnancy, spontaneous abortion, pregnancy termination, stillbirth); to be treated as competing events • Receipt of another dose of COVID-19 vaccine other than Pfizer-BioNTech bivalent COVID-19 Vaccine
Birth outcomes		
Major congenital malformations	Birth	Earliest of the following (in the infant): 
 • Diagnosis of major congenital malformation • End of the study period • End of data availability • Death • 12 months after birth
Small size for gestational age	Birth	Earliest of the following (in the infant): 
 • Diagnosis of small size for gestational age • End of the study period • End of data availability • Death • 1 month after birth

COVID-19 = coronavirus disease 2019.

090177e19f732934\Approved\Approved On: 14-Dec-2023 13:35 (GMT)

9.3. Variables

9.3.1. Vaccine exposures

Receipt of Pfizer-BioNTech bivalent COVID-19 Vaccine and other COVID-19 vaccines will be identified in claims and/or electronic health records data via pharmacy dispensing and/or procedure codes. Where quality data from existing linkages with immunization registries are available for use in research studies, immunization registry data will also be used to identify receipt of COVID-19 vaccines.

9.3.2. Safety events

All safety events of interest (ie, general safety events, pregnancy outcomes, and birth outcomes) will be identified in claims and electronic health records (where available, as not all data RPs may have access to structured electronic health records data) using diagnosis codes, with procedure and/or pharmacy dispensing codes as appropriate. Detailed definitions will be included in the SAP.

To the greatest extent possible, validated algorithms will be used for the study, if available. There are currently no plans for medical record or clinical validation of study outcomes, as validation of myocarditis/pericarditis (the primary outcome of interest) is being conducted in study C4591009 and in other studies led by other research groups.

If the algorithm for myocarditis/pericarditis has demonstrated adequate performance characteristics in other relevant validation studies (using predefined criteria, eg, a minimum positive predictive value [PPV], that will be defined in the SAP), then all algorithm-identified cases will be included in the final analysis without additional analysis to adjust for outcome misclassification. If the algorithm has not demonstrated adequate performance in prior validation studies, then the validation results (eg, PPVs) from other studies will be used to inform or adjust risk ratios (RRs) in sensitivity analysis.

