9.5. Study size

9.5.1. Self-controlled Risk Interval (SCRI) Design

Because an SCRI design will be used, statistical power for general safety events depends on the total number of events in the risk and control intervals combined, the ratio of the duration of the risk and control intervals, and the IRR. Table 8 presents the statistical power that can be obtained for a range of incidence rate ratios and sample sizes, for a 2-sided alpha = 0.05 level test, using an SCRI design with risk and control intervals of equal duration ([Musonda et al., 2006](#)). For example, 80 events will provide 86% power to detect incidence rate ratios equal to or greater than 2.0.

Table 8. Study size calculations for self-controlled risk interval design

Total events	Incidence rate ratio	Power
20	1.4	0.11
	1.6	0.17
	1.8	0.25
	2.0	0.32
	2.2	0.39
	2.4	0.46
40	1.4	0.18
	1.6	0.31
	1.8	0.44
	2.0	0.57
	2.2	0.68
	2.4	0.76
80	1.4	0.32
	1.6	0.55
	1.8	0.73
	2.0	0.86
	2.2	0.93
	2.4	0.97
100	1.4	0.39
	1.6	0.64
	1.8	0.83
	2.0	0.93
	2.2	0.97
	2.4	0.99

090177e19f732934\Approved\Approved On: 14-Dec-2023 13:35 (GMT)

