	Sensitivity analysis: quantitative bias analysis to correct comparative risk estimates for outcome misclassification	SCRI	IRRs	Sensitivity analysis to address potential misclassification of outcomes in claims data; to be implemented for myocarditis/pericarditis, if the algorithm is demonstrated to have inadequate performance in other validation studies. Such analysis may also be considered for other general safety events that have signaled in other studies.

090177e19f732934\Approved\Approved On: 14-Dec-2023 13:35 (GMT)

Table 10. Summary of planned analyses

Type of safety event	Analysis	Study design	Results	Notes on main purpose of analysis/difference from primary analysis
Pregnancy and birth outcomes	Primary analysis	Cohort: exposed vs unexposed	Descriptive; IRRs or HRs; PORs	N/A
	Subgroup analyses in populations of interest (immunocompromised individuals, individuals with history of severe COVID-19, and among subgroups defined by age)	Cohort	Descriptive, IRRs or HRs; PORs	Subgroup analyses
	Sensitivity analysis: restrict to population with linkages to immunization registries	Cohort: exposed vs unexposed	IRRs, PORs	Sensitivity analysis to address potential misclassification of unexposed status due to incomplete capture of COVID-19 vaccines in claims data; only to be performed if feasible
	Sensitivity analysis: quantitative bias analysis to correct comparative risk estimates for exposure misclassification	Cohort: exposed vs unexposed	IRRs, PORs	Sensitivity analysis to address potential misclassification of unexposed status due to incomplete capture of COVID-19 vaccines in claims data; to be considered if exposure misclassification is not sufficiently addressed in other analyses
	Sensitivity analysis: restrict to pregnant women who have a recorded history of monovalent COVID-19 vaccine before the index date	Cohort: exposed vs unexposed	IRRs, PORs	Sensitivity analysis to address potential confounding and misclassification of unexposed status in claims data
	Sensitivity analysis: quantitative bias analysis to correct comparative risk estimates for outcome misclassification	Cohort: exposed vs unexposed	IRRs, PORs	Sensitivity analysis to address potential misclassification of outcomes in claims data; analysis to be considered for pregnancy and birth outcomes that have signaled in other studies.

COVID-19 = coronavirus disease 2019; IRR = incidence rate ratio; N/A = not applicable; POR = prevalence odds ratio; SCRI = self-controlled risk interval.

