9.7.3.4. Outcome misclassification

Outcome misclassification is possible due to the use of claims and structured electronic health records to identify safety events of interest. If the performance of the algorithm for myocarditis/pericarditis has not been demonstrated to be adequate in prior validation studies, quantitative bias analysis (as described in Section 9.3.2) will be performed on comparative risk estimates for myocarditis/pericarditis using algorithm validation results from Study C4591009 if the results are applicable to this study; if the results from Study C4591009 are not applicable to this study, then algorithm validation results from other studies may be used.

Quantitative bias analysis of comparative risk estimates for other study outcomes may be considered if safety signals are observed in other surveillance systems or studies.

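### Bias analysis for myocarditis/pericarditis is switched off once an external criterion such as a minimum PPV is met, but an overall PPV does not by itself limit the bias in a self-controlled rate ratio

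*Protocol*

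**What the plan says.** Section 9.3.2 calls myocarditis/pericarditis the primary outcome of interest and sets a two-branch rule for it.

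- **Adequate branch.** Adequacy is judged from other studies, "using predefined criteria, eg, a minimum positive predictive value [PPV], that will be defined in the SAP". If the criterion is met, "then all algorithm-identified cases will be included in the final analysis without additional analysis to adjust for outcome misclassification".
- **Other branch.** If adequacy has not been shown, "then the validation results (eg, PPVs) from other studies will be used to inform or adjust risk ratios (RRs) in sensitivity analysis".

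The study adds no evidence of its own: "There are currently no plans for medical record or clinical validation of study outcomes".

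The same gate appears in four other places. Section 9.7.3.4 says that, where adequacy has not been demonstrated, "quantitative bias analysis (as described in Section 9.3.2) will be performed on comparative risk estimates for myocarditis/pericarditis using algorithm validation results from Study C4591009", with other studies as the fallback source. Table 10 in Section 9.7 lists the SCRI row "Sensitivity analysis: quantitative bias analysis to correct comparative risk estimates for outcome misclassification" and ties it, for this outcome, to shown inadequacy. Section 9.9 repeats the commitment for the case where adequacy has not been demonstrated. The abstract carries the same condition, but there the analysis is only optional (may), whereas 9.7.3.4 and 9.9 commit to it (will).

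**The concern.** Only the adequacy threshold is deferred to the SAP. The consequence of passing it, that no misclassification analysis is run, is fixed in the protocol.

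In an SCRI analysis one algorithm supplies the cases in both intervals. False positives unrelated to vaccination fall in the two intervals in proportion to their length. When the true IRR exceeds 1, the risk interval then has the higher PPV and the control interval the lower one, and the ratio is pulled toward 1. An overall PPV averages over this difference, so an algorithm can pass on it while the ratio is still materially diluted.

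Attenuation in a safety study reads as reassurance. The protocol recognises attenuation elsewhere, for over-long risk intervals (9.7.3.1) and for missed vaccinations in the pregnancy cohort (9.9). It does not carry that reasoning over to false-positive outcomes in the SCRI analysis.

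**Working it through.** **Inputs.** From Section 9.5.1: the power table is "for a 2-sided alpha = 0.05 level test, using an SCRI design with risk and control intervals of equal duration", and "80 events will provide 86% power to detect incidence rate ratios equal to or greater than 2.0". The protocol states no PPV and no adequacy threshold, and Section 9.2.1.1 leaves control intervals to the SAP. Assumptions made here: overall PPV *P* from 0.9 down to 0.5; equal intervals as in Table 8; false positives at a constant daily rate unrelated to vaccination, except in step 4.

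**1. The plan's own figure.** Let r = 0.5 be the risk interval's share of time, ρ the IRR and p = ρr/(ρr + 1 − r). The signed-root likelihood-ratio formula is:

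- A = 2[p ln ρ − ln(ρr + 1 − r)]
- B = (ln ρ)²/A × p(1 − p)
- power = Φ((√(nA) − 1.96)/√B)

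For ρ = 2 and n = 80: A = 2(0.4621 − 0.4055) = 0.1133, B = 0.94, and power = Φ((3.01 − 1.96)/0.97) = 0.860. The stated 0.86 is reproduced, and all 24 cells of Table 8 agree within 2 points.

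**2. Dilution of a true IRR R = 2.0.** Set the coded cases to 1. True cases P split R:1, and false positives (1 − P) split evenly:

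observed IRR = [P·R/(1+R) + (1−P)/2] / [P/(1+R) + (1−P)/2]

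| P | Risk | Control | Observed IRR | PPV risk / control | Power, 80 coded events |
|---|---|---|---|---|---|
| 0.9 | 0.600 + 0.050 | 0.300 + 0.050 | 1.86 | 0.923 / 0.857 | 0.78 |
| 0.8 | 0.533 + 0.100 | 0.267 + 0.100 | 1.73 | 0.842 / 0.727 | 0.67 |
| 0.7 | 0.467 + 0.150 | 0.233 + 0.150 | 1.61 | 0.757 / 0.609 | 0.56 |
| 0.6 | 0.400 + 0.200 | 0.200 + 0.200 | 1.50 | 0.667 / 0.500 | 0.43 |
| 0.5 | 0.333 + 0.250 | 0.167 + 0.250 | 1.40 | 0.571 / 0.400 | 0.32 |

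The dilution grows with the true effect: R = 3.0 is observed as 2.64 at P = 0.9 and 2.33 at P = 0.8.

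**3. The same relation read backwards.** With equal intervals, an observed 2.0 corresponds to:

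- P = 0.9: (2 − 0.15)/(1 − 0.15) = 2.18
- P = 0.8: (2 − 0.30)/(1 − 0.30) = 2.43

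With the 7-day risk interval of Table 5 and an assumed 21-day control interval, an observed 2.0 means counts in the ratio 14:21, total 35. At P = 0.9 the 3.5 false positives split 0.875:2.625, giving (13.125/7)/(18.375/21) = 2.14. At P = 0.8 the 7 split 1.75:5.25, giving (12.25/7)/(15.75/21) = 2.33.

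**4. Direction.** The observed ratio is a weighted average of the true IRR and the false-positive rate ratio between intervals. If that second ratio is 1, the result is step 2. If it exceeds the true IRR, the bias is upward. For example, take R = 2.0, P = 0.8 and an assumed false-positive ratio of 3: (0.533 + 0.150)/(0.267 + 0.050) = 2.16. The same overall PPV of 0.8 therefore goes with 1.73 or 2.16, depending on the pattern.

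**5. How a PPV is used in the correction** (P = 0.8, observed 1.73, constant false-positive rate):

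- Common multiplier: (0.8 × 0.633)/(0.8 × 0.367) = 1.73, unchanged.
- Interval-specific PPVs: (0.842 × 0.633)/(0.727 × 0.367) = 2.00.
- Subtracting false positives by interval length: (0.633 − 0.100)/(0.367 − 0.100) = 2.00.

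**The case against.** The strongest reply is that the protocol does address outcome misclassification. A reader might infer from the quoted rule that dilution of the primary outcome is never corrected. That does not stand: where adequacy is not shown, Sections 9.3.2, 9.7.3.4 and 9.9 and Table 10 all plan a bias analysis, with a named source and a fallback.

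A reader might also infer that the planned correction multiplies both counts by one PPV and so does nothing. The text does not say this. It speaks of validation results, offers PPVs in the plural as an example, and gives no formula. Step 5 shows that even a single overall PPV works if it is used to remove false positives by interval length. The form of the correction can properly be left to the SAP.

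Nor do the documents support treating bias toward 1 as certain. That rests on false positives being unrelated to vaccination.

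Finally, the lower rows of the table in step 2 may fall in the branch where an analysis is planned, so they need not illustrate uncorrected bias. Since no threshold is stated, this cannot be settled from the protocol.

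All of this narrows the point. It leaves the adequate branch, where the protocol itself rules out any check.

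**Conclusion.** The point holds in limited form. Once an external criterion is met, no misclassification analysis is done for the outcome the protocol calls primary, and an overall PPV, the one example given, does not show that the SCRI ratio is nearly unbiased.

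At PPVs that could plausibly pass (0.9 and 0.8, assumed), a true IRR of 2.0 would be seen as about 1.86 and 1.73. These figures rest on equal intervals and a constant false-positive rate. Differential work-up or coding after vaccination could reverse the direction, which is itself a reason to examine the bias whichever branch applies.

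In the other branch the plan is not wrong but open: a common multiplier would satisfy its wording and leave the IRR unchanged. The difference between may in the abstract and will in 9.7.3.4 and 9.9 is a small inconsistency. This merits a change but does not invalidate the primary analysis.

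**What to change.** In Sections 9.3.2, 9.7.3.4 and 9.9 and Table 10, remove the adequacy condition for myocarditis/pericarditis. State that a quantitative bias analysis of its IRR will always be reported as a sensitivity analysis, and specify that it will:

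- use PPVs specific to the risk and control intervals where they exist;
- otherwise subtract false positives in proportion to interval length, over a stated range of overall PPV;
- include one scenario with more false positives soon after vaccination;
- not apply one PPV as a common multiplier to both intervals.

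Align the abstract's optional wording with the commitment in 9.7.3.4 and 9.9. The primary IRR remains based on all coded cases.

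The cost is wording and a small calculation on counts already produced, with no new data. The downside is one extra estimate that depends on an assumed false-positive pattern and should be labelled so.
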